1 INTRODUCTION

This Statistical Analysis Plan (SAP) describes the statistical methodology and analysis to be performed based on Alnylam Pharmaceuticals, Inc., Protocol ALN-GO1-001 (Original, 18 December 2015; Amendment 1, 01 July 2016; Amendment 2, 21 September 2016; Amendment 3, 09 December 2016; and Amendment 4, 27 June 2017). Any deviations from this analysis plan will be substantiated by sound statistical rationale and will be documented in the final clinical study report.

2 STUDY OBJECTIVES

2.1 Primary Objective

• Evaluate the safety and tolerability of single- and multiple-ascending doses of ALN-GO1, respectively, in healthy adult subjects and in patients with Primary hyperoxaluria type 1 (PH1)

2.2 Secondary Objectives

- Characterize the pharmacokinetics (PK) of ALN-GO1
- Evaluate the pharmacodynamics (PD) of ALN-GO1

2.3 Exploratory Objectives

3 STUDY OVERVIEW

3.1 Summary of Study Design

This is a randomized, single-blind, placebo-controlled study of subcutaneously administered ALN-GO1. The study is designed to evaluate the safety, tolerability, PK, and PD of single- and multiple-ascending doses of ALN-GO1 and will be conducted in 2 parts:

- Part A: single-ascending dose (SAD) part in healthy adult subjects, followed by
- Part B: multiple-ascending dose (MAD) part in adult and pediatric patients with PH1

The study will be conducted in a single-blind manner, with the Investigators, SRC, and Sponsor unblinded to permit ongoing unblinded review of safety, tolerability, PK, and PD data. Part A will be conducted at 1 clinical study center in the UK. Part B is expected to take place at approximately 12 clinical study centers worldwide.

The study design is summarized in Figure 1.

[figure not shown]

Figure 1: Study Design

3.1.1 Single-ascending Dose Part in Healthy Adult Subjects (Part A)

Part A is the single-ascending dose part of the study in healthy adult subjects. Subjects will be enrolled in 1 of 3 ascending dose cohorts, with the possibility for 2 additional optional cohorts. Each cohort will be comprised of 8 subjects randomized 3:1 to ALN-GO1 or placebo (study drug).

Subjects will be screened from -45 to -2 days before study drug administration. Subjects will be admitted to the clinical study center on Day -1 to determine continued eligibility and for predose assessments. Subjects in each cohort will be randomized on Day 1 and will receive 1 SC dose of study drug. Subjects will be discharged from the clinical study center on Day 2 after completing the 24-hour postdose follow-up assessments.

Subjects will return to the clinical study center on an outpatient basis for safety, tolerability, PK, and PD monitoring at time points specified in the Schedule of Assessments through the last postdose follow-up visit (Day 57). Safety and PD follow-up will continue: 1) for at least 57 days, and 2) until plasma glycolate decreases to a level that is no more than 20% above of baseline or until plasma glycolate is below the upper limit of normal (≤14 nmol/mL).

3.1.2 Multiple-ascending Dose Part in Patients with Primary Hyperoxaluria Type 1 (Part B)

Part B is the multiple-ascending dose part of the study in up to 24 adult and pediatric patients with PH1 with relatively well-preserved renal function. The overall allowable age range of the patients in Part B will be 6-64 years.

^a Patients in Part B will be invited to participate in an open-label extension study provided they meet the criteria described in Protocol ALN-GO1-001 Section 4.1.2 (Amendment 4; 27 June 2017).

Two mandatory ascending dose cohorts will be enrolled, with the possibility to also enroll up to 3 additional optional cohorts to further explore the optimal dose or regimen. Each cohort will be comprised of 4 patients, randomized 3:1 to ALN-GO1 or placebo. Up to 2 cohorts in Part B may be expanded by up to 4 additional patients (these patients will all receive ALN-GO1, not placebo).

Patients will be screened within 45 days prior to study drug administration. Baseline urinary oxalate excretion and creatinine clearance will be assessed through 24-hour urine collections. Patients will be randomized between Day -1 and Day 1 and will receive the first dose of ALN-GO1 or placebo on Day 1. The 24- and 48-hour postdose follow up assessments will take place on Day 2 and Day 3. Patients who receive study drug monthly will return to the clinical study center for safety, tolerability, PK, and PD monitoring at time points specified in the Schedule of Assessments (Protocol ALN-GO1-001 Table 2; Amendment 4, 27 June 2017) for the remaining 2 single-blind doses of study drug (through Day 57). After completion of the blinded portion of the study, patients dosed monthly will be unblinded (on or after Day 78). Patients who initially received placebo will then receive ALN-GO1 at the same dose administered to the cohort into which they were initially randomized and will follow the assessment schedule as indicated (Protocol ALN-GO1-001 Table 3; Amendment 4, 27 June 2017).

After the dosing period, patients will return to the clinical study center for continued safety, tolerability, PK, and PD monitoring through the last postdose follow-up visit. Following completion of the postdose follow-up period, patients will be invited to participate in an open-label extension study provided that:

- Urinary oxalate is above the ULN and patients meet at least 1 of the following criteria:
 - One 24-hour urinary oxalate value is >80% of baseline.
 - Two 24-hour urinary oxalate values are above the midpoint between their baseline and nadir 24-hour urinary oxalate values. The nadir must be from a valid collection after all doses are administered.
 - At least 12 months have elapsed from time of final dose administration.

For patients who do not enroll in the open-label extension study, safety and PD follow up will continue until:

- 24-hour urinary oxalate is >80% of baseline, AND
- Plasma glycolate is <20% above baseline or \le the ULN

3.2 Study Assessments

The complete Schedule of Assessments is found in Table 1 (Single-ascending Dose Cohorts in Healthy Subjects (Part A)), Table 2 (Multiple-ascending Dose Cohorts in Patients with Primary Hyperoxaluria Type 1 (Part B – Monthly Dosing)), Table 3 (Multiple-ascending Dose Cohorts in Patients with Primary Hyperoxaluria Type 1 (Part B) who Previously Received Placebo and will Receive Open-Label ALN-GO1 – Monthly Dosing), and Table 4 (Multiple-ascending Dose

Cohorts in Patients with Primary Hyperoxaluria Type 1 (Part B – Quarterly Dosing)) of Protocol ALN-GO1-001 (Amendment 4; 27 June 2017).

3.3 Duration of Treatment and Overall Duration of Study

The duration of the study is as follows:

• Part A: The estimated total time on study, inclusive of screening, for each subject is up to 405 days. The duration of treatment is a single dose.

• Part B:

- For patients dosed monthly: The duration of treatment for patients initially randomized to receive active study drug is 57 days. The estimated total time on study, inclusive of screening, for each patient is up to 462 days. Additionally, the duration of treatment for patients initially randomized to receive placebo is 141 days. The estimated total time on study, inclusive of screening, for each patient initially randomized to receive placebo, then active study drug, is up to 546 days.
- For patients dosed quarterly: The duration of treatment is 85 days for patients randomized to placebo and active study drug. The estimated total time on study, inclusive of screening, is up to 490 days.

The overall duration of the study is estimated to be 4 years, including enrollment.

3.4 Study Populations

In Part A, the study population will consist of healthy adult volunteers ages 18 years and older.

In Part B, the study population will consist of pediatric and adult patients (ages 6 years - 64 years inclusive) that have a confirmed diagnosis of PH1.

Additional information regarding specific inclusion and exclusion criteria are listed in Protocol ALN-GO1-001 Section 5.1 and 5.2 (Amendment 4; 27 June 2017).

3.5 Study Centers

The single-ascending dose (SAD) part in healthy adult subjects (Part A) will be conducted at 1 clinical study center in the United Kingdom. The multiple-ascending dose (MAD) part in patients with PH1 (Part B) is expected to take place at approximately 12 clinical study centers worldwide.

3.6 Randomization and Blinding

This is a randomized, single blind, placebo-controlled study; therefore, only the study subjects/patients will be blinded to treatment assignment. In Parts A and B, after confirmation of eligibility, during screening, and upon admission the clinical study center, subjects/patients will

be assigned to a dose cohort and randomized in a 3:1 ratio (ALN-GO1:placebo). No subject/patient will be a member of more than 1 cohort. A unique subject/patient identification number, incorporating the clinical study center number, will be assigned sequentially to the subject/patient.

The clinical study center pharmacy staff will randomize the subject/patient in accordance to a cohort-specific randomization list generated by the biostatistician at the Contract Research Organization (CRO) for appropriate dispensation of the study drug.

Patients in Part B dosed monthly will be unblinded on or after Day 78 in order for patients and their families to be better prepared for the transition to receive ALN-GO1 if initially randomized to placebo. Patients dosed quarterly will be unblinded to initial treatment assignment following completion of the postdose follow-up period. The Investigators, Medical Monitors at the Sponsor and CRO, clinical study center personnel, pharmacokineticist, and members of the SRC will have knowledge of the treatment assignment. The clinical study center pharmacy staff will maintain the single-blind according to clinical study center-specific procedures and the Pharmacy Manual. Syringes containing dispensed study drug will be masked in the pharmacy before transfer to the clinic.

During the blinded period, if the subject/patient becomes seriously ill during the study, and the treating physician determines that the clinical management of the subject requires that the subject know the study drug assignment, the Investigator may break the blind, as necessary.

Based on SRC review of accumulated safety, tolerability, and PD data, 3 additional cohorts may be enrolled and dosed according to the same eligibility criteria in Part B to better define safety or PD effects. Additional cohorts may be enrolled at higher, lower, or intermediate dose levels, but will not exceed the maximum administered dose of 6 mg/kg, and will follow the protocol-specified dose escalation criteria.

Based on SRC review of accumulated safety, tolerability, and available PD data, up to 2 cohorts in Part B may be extended by up to 4 additional patients based on study progression and stopping rules. These patients will all receive active drug, not placebo.

4 STATISTICAL METHODOLOGY

Unless stated otherwise, the methodology described in this section will apply to both Part A and Part B of this study. Data from Part A and Part B will be analyzed separately.

Summary analyses will be presented as follows. The primary analyses will be presented in order of ascending ALN-GO1 dose with the placebo group presented first. Patients randomized to placebo will be pooled across enrollment cohorts for all analyses where applicable.

4.1 Sample Size Determination

The sample size was determined on the basis of clinical considerations rather than power calculations. Up to a total of 64 participants (40 subjects in Part A, 24 patients in Part B) are planned to be enrolled in this study, including optional and expansion cohorts.

4.2 Analysis Populations

The following analysis populations will be considered for the purposes of data analysis.

4.2.1 Safety Analysis Set

For both Part A and Part B, the Safety Analysis Set will include all subjects who received at least 1 dose of study drug (placebo or ALN-GO1).

The Safety Analysis Set will be used for safety analyses. Subjects will be summarized according to the treatment actually administered.

4.2.2 Pharmacokinetic Analysis Set

The PK Analysis Set will include all subjects/patients who receive at least 1 dose of study drug and have at least 1 postdose sample for PK parameters and who have evaluable PK data.

The PK analysis will be based on the PK Analysis Set.

4.2.3 Pharmacodynamic Analysis Set

The PD Analysis Set will include all subjects/patients who receive at least 1 dose of study drug and who have at least 1 postdose blood and/or urine sample evaluable for PD parameters.

PD summaries will be based on the PD Analysis Set.

4.3 General Statistical Considerations

The primary goal of the study is to evaluate the safety and tolerability of ALN-GO1 in healthy adult subjects and patients diagnosed with PH1. The data cutoff date for the primary analysis will occur after all subjects have either discontinued the study or completed all safety follow-up assessments (as in Section 3.2).

Continuous data will be described using descriptive statistics including the number of observations (n), mean, standard deviation, median, minimum, and maximum. Categorical and ordinal data will be described using the subject/patient count and percentage in each category. For the summary statistics of all numerical variables unless otherwise specified, minimum and maximum will be displayed to the same level of precision as reported. Mean, median, and standard deviation will be displayed to one level of precision greater than the data collected. Summary tables will present results by cohort for each ALN-GO1 dose in ascending dose order, total (all subjects receiving ALN-GO1), and placebo, where the placebo subjects/patients will be

combined across dose cohorts. Data will be displayed in all listings sorted by study part and cohorts with placebo ordered last.

Subjects/patients will be identified in the listings by the subject/patient identification number concatenated with the investigator number.

When count data are presented, the percentage will not be presented when the count is zero in order to draw attention to non-zero counts. A row denoted "Missing" will be included in tabulations where specified on the shells to account for dropouts and missing values. The denominator for all percentages will be the number of non-missing values in that cohort/treatment, unless otherwise specified.

If the assessment date is after the date of first study drug dose The study day will be calculated as:

Study day = Date of assessment – date of first dose of study drug + 1,

otherwise if assessment date is before the date of the first dose of study drug then study day will be calculated as:

Study day = Date of assessment - date of first study drug dose.

4.3.1 Baseline Definition

The baseline value is defined as the last non-missing value before the first dose of the randomized study drug, unless otherwise specified.

In Part B, for patients who are randomized initially to placebo, the baseline value for the placebo dosing period is defined as the last non-missing value before the first dose of placebo. For these patients, their baseline value for the open-label ALN-GO1 period is defined as the last non-missing value before the first dose of ALN-GO1.

4.3.2 Multicenter Studies

Part A will take place at a single study center.

Part B will take place at multiple centers but the center effect will not be considered for the planned descriptive analysis. Data will not be stratified by study center for reporting of descriptive statistics.

4.3.3 Multiple Comparisons

No adjustments for multiple comparisons will be made for the planned descriptive analysis.

4.3.4 Missing Data

Unrecorded data values will be recorded as missing. Only recorded (i.e. non-missing) data values will be used for reporting of descriptive statistics unless otherwise stated.

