After the dosing period, patients will return to the clinical study center for continued safety, tolerability, PK, and PD monitoring for at least 12 weeks (84 days) following the last dose of study drug. Following completion of the 12-week postdose follow-up period, patients will be invited to participate in an open-label extension study.

For patients who do not enroll in the open-label extension study, safety and PD follow up will continue until 24-hour urinary oxalate is $>80\%$ of baseline, and plasma glycolate is $<20\%$ above baseline or \leq the ULN. If an investigator wishes to discontinue follow up after completion of the postdose follow-up period and prior to oxalate and glycolate recovery, the SRC must agree based upon consideration of emerging data on the safety of ALN-GO1 knockdown and the individual patient's safety and PD data.

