7.2.3 By-visit Data Presentation

In Part B, the by-visit PD and safety summaries will be presented according to the specifications below.

Monthly Dosing Regimen: Part B

Timepoint ^a	Placebo ^b	Monthly	Monthly	Monthly	Monthly	Monthly	Monthly
	(N=4)	ALN-GO1	ALN-GO1	ALN-GO1	ALN-GO1	ALN-GO1	ALN-GO1
		Single-blind ^c	Comb.d	Single-blind ^c	Comb.d	Single-blind ^c	Comb.d
		Dose1	Dose1	Dose2	Dose2	Total	Total
		(N=3)	(N=4 or 8)	(N=3)	(N=4 or 8)	(N=6)	(N=8 or 16)
Baselinee							
Day 29							
Day 57							
Day 85 ^f							
Day 113	NA						
Day 141	NA						
Day 169 ^g	NA						
Day 197 ^h	NA						
Day 225	NA						
Day 253	NA						
Day 281	NA						
Day 309	NA						

- a: In monthly dosing regimen, patients randomized to ALN-GO1 will be summarized by study day 1 to 85 during the single-blind monthly treatment period, then by post dosing follow-up period after Day 85 and up to Day 169, followed by Safety and PD follow-up after Day 169. Patients randomized to Placebo will be summarized by study day 1 to 85 relative to placebo dosing date during the single-blind treatment period. Data collected after the first dose of ALN-GO1 will be summarized separately by days relative to the first open-label ALN-GO1 dose with all visits for the rest of the study mirrored to the patients randomized to the single-blind ALN-GO1. These data will be summarized in combination with data from patients randomized to ALN-GO1 at each corresponding visit.
- b: Patients from all monthly and quarterly dosing cohorts randomized to placebo at study start
- c: Patients randomized to ALN-GO1 at study start receiving ALN-GO1 in single-blind manner
- d: Patients receiving ALN-GO1 in single-blind or open-label manner and in any sequence combined
- e: Baseline is defined as before first dose date/time of each treatment, placebo or ALN-GO1
- f: Day 85 is the end of treatment period
- g: Day 169 is the end of post-treatment follow-up period
- h: Day 197 and later visits are Safety and PD follow-up visits

Quarterly Dosing Regimen: Part B

Timepointa	Placebob	Quarterly	Quarterly	Quarterly	Quarterly	Quarterly	Quarterly	Quarterly	Quarterly	Quarterly
	(N=4)	2-doses ^c	1-dose ^d	Comb.e	2-doses ^c	1-dose ^d	Comb.e	2-doses ^c	1-dose ^d	Comb.e
		ALN-GO1	ALN-GO1	ALN-GO1	ALN-GO1	ALN-GO1	ALN-GO1	ALN-GO1	ALN-GO1	ALN-GO1
		Dose1	Dose1	Dose1	Dose2	Dose2	Dose2	Total	Total	Total
		(N=3)	(N=1)	(N=4)	(N=3)	(N=1)	(N=4)	(N=6)	(N=2)	(N=8)
Baselinef										
Day 29										
Day 57										
Day 85g										

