7.6 Pharmacodynamic and Exploratory Analyses

Pharmacodynamic parameters will be measured from blood and urine samples collected at times outlined in the Schedule of Assessments in both Part A and Part B. PD analyses will be based on the Pharmacodynamic Analysis Sets.

24-hour urine oxalate content corrected for BSA will be calculated as:

[24-hour urine oxalate in mmol/L]*[24-hour urine volume recorded in CRF in ml] /(1000 ml per L)*24hours/[actual collection time calculated from CRF in hours] *1.73/[patient BSA]

Where patient BSA will be calculated as:

Patient BSA = sqrt([mean height in cm] *[weight in kg]/3600).

24-hour urine creatinine clearance corrected for BSA will be calculated as:

[24-hour urine creatinine concentration in mg/dl]*[24-hour urine volume recorded in CRF in ml]

/[Plasma creatinine in mg/dl]/[actual collection time calculated from CRF in minutes] *1.73/[patient BSA]24-hour urine oxalate/creatinine ratio will be calculated as:

24-hour urine oxalate concentration (mg/L) /24-hour urine creatinine concentration (mg/dL)/10.

For Part A and Part B, the mean and standard error of actual values and changes from baseline in plasma and urine glycolate will be plotted over time by ALN-GO1 dose level and placebo. In

addition, plots will be provided for plasma and urine glycolate of individual subjects by dose level of ALN-GO1 and placebo.

For Part B, the mean and standard error of actual values and changes from baseline in urinary oxalate per 24-hour urine collection and urinary creatinine per 24-hour urine collection will be plotted over time. In addition, the plots will be presented separately by ADA status. Plasma glycolate concentration and oxalate/creatinine ratio will be plotted in the same manner. For patients randomized to placebo, figures will include PD measurements up to the first dose of open-label study drug.

For other PD variables in Part A and B, descriptive statistics will be provided for actual results, change from baseline, and percent change from baseline. For Part B, the PD summaries will be presented according to the data display specification in Section 7.2.3.For Part A and Part B, Cmax and AUCt of plasma glycolate will be presented with descriptive statistics and percent coefficient of variation [%CV]) by regimen and ascending dose level and placebo presented first.

In Part A and Part B, all PD data will be listed by regimen, dose, ADA status (Part B only) and subject/patient.

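### Late Part B by-visit PD means average only the patients still followed, and under the exit rules in the SAP that group is selected on oxalate recovery

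*SAP*

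**What the plan says.** SAP 4.3.4 gives one rule for missing data: "Only recorded (i.e. non-missing) data values will be used for reporting of descriptive statistics unless otherwise stated". SAP 7.6 adds: "For Part B, the PD summaries will be presented according to the data display specification in Section 7.2.3". The tables in SAP 7.2.3 have a row every 28 days from Day 29 to Day 309, and a footnote to the monthly table states "Day 197 and later visits are Safety and PD follow-up visits". SAP 7.6 also plans plots of mean and standard error over time for urinary oxalate and for glycolate.

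The SAP covers the protocol up to "and Amendment 4, 27 June 2017". Its section 3.1.2 therefore allows rollover only if oxalate is above the ULN and one of three criteria is met:
- "One 24-hour urinary oxalate value is >80% of baseline";
- two values above the midpoint between baseline and nadir;
- 12 months since the last dose.

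Patients who do not roll over stay until oxalate and plasma glycolate have both recovered.

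Protocol 4.1.2, now at Amendment 5, keeps that last rule: "safety and PD follow up will continue until 24-hour urinary oxalate is" above 80% of baseline and glycolate has also recovered, unless the Safety Review Committee agrees to an earlier stop. It drops the oxalate thresholds for rollover: "Following completion of the 12-week postdose follow-up period, patients will be invited to participate in an open-label extension study".

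The SAP plans no time-to-recovery summary and no sensitivity analysis for this attrition. Protocol 8.2.3 leaves sensitivity work on missing data optional.

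**The concern.** A mean of recorded values at a late visit describes only the patients still in follow-up. If they are still there because their oxalate has not come back, the quantity being averaged decides who is averaged. With dose columns planned at one to eight patients (SAP 7.2.3), a single departure can move a row.

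A hypothetical case shows the mechanism. Four patients at 50, 60, 85 and 90% of baseline average 71%. The last two meet the exit rule and leave. If each patient then rises by 5 points, the mean of all four is 76%, but the tabulated mean is (55 + 65)/2 = 60%. The table shows suppression deepening while every patient is recovering.

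What is at stake is the shape of the recovery curve. Part B has optional cohorts to explore dose and regimen, and a reader will look at these rows and plots to judge how long the effect lasts.

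**Working it through.** **1. Which rows are exposed.** Required follow-up ends 84 days after the last dose (Protocol 4.1.2).
- Monthly: 57 + 84 = Day 141. For placebo-first patients it is 141 + 84 = Study Day 225, which is 225 − 85 + 1 = Day 141 relative to ALN-GO1.
- Quarterly, two doses: 85 + 84 = Day 169.
- Quarterly, placebo first, one dose on Study Day 85: Study Day 169, which is 169 − 85 + 1 = Day 85 relative to ALN-GO1.

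The exposed rows in SAP 7.2.3 are therefore monthly Day 169 to 309 (6 rows), two-dose quarterly Day 197 to 309 (5 rows) and one-dose quarterly Day 113 to 309 (8 rows). Earlier rows are not affected by these exits. SAP 7.2.3 labels Day 169 as the end of monthly post-treatment follow-up, whereas Protocol Table 2 ends it on Day 141.

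**2. Whether exit depends on oxalate within the table.** The only rollover criterion in SAP 3.1.2 based on time is 12 months after the last dose. That falls at 57 + 365 = Day 422 (monthly), 85 + 365 = Day 450 (two-dose quarterly) or 1 + 365 = Day 366 (one-dose, relative to ALN-GO1), all after Day 309. So up to Day 309 every rollover or completion route in the SAP requires some oxalate recovery. Under Amendment 5, rollover does not; only the exit of patients who do not roll over still does.

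**3. Size.** The documents give no recovery or rollover rates, so these inputs are assumptions. Virtual patients had 28-day visits from Day 85 to Day 309, exponential recovery, 15% within-patient CV, glycolate at 3 to 5 times baseline returning at the same rate, and oxalate always above the ULN. The route of glycolate at or below the ULN was left out; including it would loosen the exit rule. The gap is the mean if everyone stayed minus the mean of those still followed, in points of baseline oxalate at Day 309.

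Set 1: Day 85 oxalate at 25 to 45% of baseline, median half-time 90 days, between-patient CV 60%. If everyone stays, the mean reduction is 13%, so the mean is 87% of baseline.

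| Exit rule | Gap | Observed mean |
|---|---|---|
| Amendment 4, 50% roll over | about 5 | 87 − 5 = 82 |
| Amendment 4, 90% roll over | about 11 | 87 − 11 = 76 |
| Amendment 5, rollover unrelated to recovery | about 3 | 87 − 3 = 84 |
| No rollover, both analytes must recover | about 3 | 87 − 3 = 84 |

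With median half-times from 60 to 150 days, the Amendment 5 gap runs from about 4 down to about 1.

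Set 2: Day 85 oxalate at 35% of baseline, between-patient log-SD 0.5.
- Amendment 4, 90% rolling over: 93 v 86 (half-life 60 days) and 87 v 78 (90 days), gaps of 7 and 9. The visit at which the mean first passes 80% moves from Day 197 to Day 253, and from Day 253 to beyond Day 309. With 50% rolling over and a 90-day half-life: 87 v 84, a gap of 3.
- Amendment 5, rollover unrelated to recovery: 93 v 88 to 90 (60 days) and 87 v 85 (90 days), gaps of 2 to 5, with no change in the 80% crossing visit.
- Rollover on time as the only exit, unrelated to recovery: 93 v 93, no bias.
- Amendment 5, slow recoverers more likely to roll over: at Day 197, 81 v 88 (60 days) and 73 v 81 (90 days). The sign reverses.
- If 90% roll over at Day 141, about 1.6 of 16 patients remain at Day 169.

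**The case against.** A reader might infer that the late rows overstate duration whichever rule applies, and by a wide margin. If oxalate recovery alone ended follow-up, the Set 1 assumptions would give a 13% true mean reduction at Day 309 against 26% observed. The documents do not support this. Without rollover, glycolate must recover too, which weakens the selection. Under the current protocol, rollover follows time since the last dose and does not by itself leave the slow recoverers behind.

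A reader might also infer that the choice between monthly and quarterly dosing rests on these rows. The documents do not say so. The Amendment 4 rationale credits Part A data for the quarterly option, the comparison with placebo ends at Day 85, duration of effect is not a named endpoint, and no hypothesis is tested.

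The plan also offers some protection. SAP 4.3 reports n with each summary, and SAP 7.6 lists all PD data by patient and plots individual glycolate. That makes attrition visible, but it does not correct a mean or a plotted curve. Finally, a Kaplan–Meier display censored at rollover inherits the problem where rollover depended on oxalate. That stands, and the display must say so.

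**Conclusion.** The concern holds in a limited form. The late Part B means are observed-case means of a group whose membership can depend on the outcome, and nothing planned deals with it. Under the Amendment 4 rules in SAP 3.1.2, suppression looks longer than it is: about 5 to 11 points at Day 309 in Set 1, and 3 to 9 in Set 2. Under Amendment 5 the gap is about 1 to 4 points if rollover is unrelated to recovery (2 to 5 in Set 2). It can take either sign if rollover is related, and the larger problem may be rows resting on one or two patients. Every magnitude depends on assumed recovery, glycolate and rollover figures. The selection mechanism and the list of exposed rows come from the documents themselves. Rows within required follow-up, including the placebo comparison through Day 85, are untouched. The change is worth making, but the primary safety analysis does not depend on it.

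**What to change.** 1. Align SAP 3.1.2, 7.2.2 and 7.2.3 with Amendment 5, including the end of monthly follow-up.
2. Limit by-visit PD means and mean plots to required follow-up, counted from the first ALN-GO1 dose: Day 141 monthly, Day 169 quarterly two-dose, Day 85 quarterly one-dose. A single Day 169 limit for all quarterly patients would keep exposed rows in the one-dose column.
3. Show later data as individual profiles, with n and reason for exit at each visit.
4. Add a descriptive summary of time to 24-hour urinary oxalate above 80% of baseline, censored at rollover. State that this censoring is informative for any patient who rolled over under Amendment 4, and may be so under Amendment 5 if the decision to roll over is related to recovery.

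The cost is SAP wording and one display. Protocol 8.2 already allows data after the dosing period to be listed instead of summarised, so no protocol change is needed. What is lost is a set of late mean rows that rest on few patients.
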